17. PUBLICATION POLICY

A meeting will be held after the end of the trial to allow discussion of the main results among the collaborators prior to publication. Results of the formative phase, pilot, trial, process evaluation and health economic evaluations will be submitted as publications in peer-reviewed journals.

The success of E-MOTIVE depends on the collaboration of a large number of healthcare providers across several countries. For this reason, all publications arising from this work will be attributed to the “E-MOTIVE Collaborative Group”, with the writing committee and order approved by the ITMG.

Any secondary publications and presentations prepared by Investigators must be reviewed and approved by the ITMG. Manuscripts must be submitted to the ITMG in a timely fashion and in advance of being submitted for publication, to allow time for review and resolution of any outstanding issues. The ITMG are also obliged, by the terms of our contract to notify the funder (Bill & Melinda Gates Foundation) before submitting any publications. Authors must acknowledge that the trial was performed with the support of The University of Birmingham and funding from the Bill & Melinda Gates Foundation (including relevant acknowledgment text that will be provided by the ITMG).

Site investigators may access the full dataset if a formal request describing the plans of the analysis is approved by the ITMG. Individual countries will be allowed to publish their efficacy results, however the publication of efficacy results from the pooled analysis will take precedence over efficacy result publications of individual countries, unless the ITMG decides otherwise.

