4.3. Randomisation

After regulatory approvals, 78 clusters from Kenya, Nigeria, South Africa and Tanzania will enter a 7-month baseline period in which they will be following usual care with dissemination of the current guidelines. After this 7-month baseline period, we will allocate 78 clusters (a 1:1 ratio) to either the E-MOTIVE intervention or usual care for 7 months, with an allowance of two months ('transition phase') for full implementation and embedding of the intervention. Clusters not allocated to E-MOTIVE will continue to follow usual care as per the baseline period for the remainder of the intervention phase.

The recruitment of all clusters will be completed within a 3-month period. Following the baseline period, randomisation will be implemented using a minimisation algorithm to ensure a balance of the intervention and control facilities for the following (measured at the cluster-level during the first 5 months of the baseline phase):

1. Number of vaginal births
2. Proportion of births with the composite primary outcome (before randomisation)
3. Oxytocin quality
4. Number of intervention and control clusters in each country

Details of how these are calculated are presented below. The minimisation will be stratified in each country (separate minimisations) to increase the balance in all of the above covariates within a country.

Number of vaginal births

After the first five months of the baseline phase has completed, for each cluster, we will gather the total number of births and the number of months of data collection to calculate the cluster's monthly birth rate. We will then use the cluster's monthly birth rate to determine the country's median birth rate. The clusters above and below the country median will form the categories for the minimisation algorithm.

The proportion of births with the composite primary outcome before randomisation

After the first five months of the baseline phase has completed, for each cluster, we will gather the total number of births and the total number of events. The ratio of the number of events to the number of births will give us the proportion of births with the composite outcome for that cluster. We will then use the cluster's primary outcome proportion to determine the country's median primary outcome proportion. The clusters above and below the country median will form the categories for the minimisation algorithm.

Oxytocin Quality

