7.4. Primary outcome analysis

The model being fitted to the binary primary composite outcome will be a mixed-effect logistic regression model with robust standard errors.

To account for clustering, random effects (for cluster and cluster-period) are included (see section 7.4.1). We will account for the time-period using fixed-effects (see section 7.4.2), and will adjust for covariates used in the randomisation in the first instance (see section 7.4.3). If there are issues with model-convergence, then a plan is in place (see section 7.4.4).

Risk ratios and risk differences will then be derived using marginal standardisation [10], as in for example a CRT by Kirkwood et al [11]. Under this approach, the mean risk under the control condition and intervention condition is obtained. The risk ratio is then derived using the mean risk in intervention condition and by the mean risk in the control condition, with the calculation

being performed on the log scale. The risk difference is derived as the mean risk in intervention condition minus the mean risk in the control condition. We will use the unconditional standard errors to obtain the confidence interval, as this allows for correlation amongst the observations [12].

A small sample correction will not be included in the main analyses as the number of clusters is expected to be sufficiently large to maintain the type I error rate [13].

The integration method used will be mean-variance adaptive Gauss-Hermite quadrature, which is the default in Stata.

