7.4.1. Accounting for clustering of observations

To allow for correlation between observations within a cluster, we will fit mixed-effect logistic regression models with robust standard errors. Clustering will be allowed for in all analyses through the use of random effects. Recent developments in the methodological literature for the design and analysis of multiple-period cluster randomised trials suggest that a simple exchangeable correlation structure is not sufficient to depict the correlation structure in multiple-period cluster randomised trials [8]. We will include a random cluster by period interaction in addition to a random cluster effect to allow for the decay in correlation between observations made in the same cluster, but at different time periods.

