7.10. Planned subgroup analyses

We will estimate and report subgroup effects irrespective of their statistical significance. The results of subgroup analyses will be treated with caution. Analysis will be limited to the primary composite outcome and key implementation outcomes only. The planned subgroup analyses are:

- Baseline period PPH rate (above median vs below median) as objectively diagnosed by blood collection drape using data from the baseline period
- Number of vaginal births (using baseline period size) (above median size vs below median size)
- Age (three levels categorised by tertiles of the distribution)
- Parity (none vs any)
- Type of pregnancy (singleton vs multiple),
- Gestational age (term vs preterm),
- Mode of birth (spontaneous vs assisted),
- Presence of any risk factors for PPH vs no risk factors for PPH (Risk factors for PPH are: diagnosis of preeclampsia, induction or augmentation of labour, previous caesarean, previous post-partum haemorrhage, antepartum haemorrhage, episiotomy, vaginal tears, retained placenta)
- Country (Kenya vs Nigeria vs South Africa vs Tanzania).
- Compliance with the bundle (facilities split into above or on median vs below median). Compliance with the MOTIVE bundle is defined as adherence with three core elements of the bundle: administration of oxytocic drugs, TXA and IV fluids. If all three core elements are administered, this will be deemed positive for bundle compliance.
- Time since intervention exposure (exposure (defined as number of months since cluster began post-randomisation phase) (described below)

Time by treatment interaction

To evaluate whether the intervention effect is consistent over time, we will estimate the time by treatment interactions. To do this, we will categorise observations made in the post-randomisation phase to: month 1; month 2; month 3; month 4; month 5; month 6; and month 7.

The analysis of the subgroups will be performed by including a treatment by subgroup interaction parameter in the regression model. Subgroup analyses that are at the cluster level (for example, country) will contain a between-within small sample correction – which is recommended when using mixed models for binary outcomes[15]. For this, we will use the t-

distribution with the appropriate degrees of freedom (number of clusters minus number of parameters estimated in the model).

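### Country subgroup (SAP 7.10): trial-wide degrees of freedom paired with an uncorrected robust standard error give country intervals that under-cover and a heterogeneity test that rejects too often

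*SAP*

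**What the plan says.** SAP 7.10 analyses subgroups by "including a treatment by subgroup interaction parameter in the regression model". It adds: "Subgroup analyses that are at the cluster level (for example, country) will contain a between-within small sample correction". The correction is a t-"distribution with the appropriate degrees of freedom (number of clusters minus number of parameters estimated in the model".

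Section 7.10 does not name the standard error. The model being extended is defined in 7.4: "The model being fitted to the binary primary composite outcome will be a mixed-effect logistic regression model with robust standard errors". Section 7.4.1 repeats it: "we will fit mixed-effect logistic regression models with robust standard errors". No section bias-corrects that robust variance, and for the main results 7.4 says: "A small sample correction will not be included in the main analyses".

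On numbers, SAP 4.3 states that "78 clusters from Kenya, Nigeria, South Africa and Tanzania will enter a 7-month baseline period". Neither document gives the number of facilities per country. Section 7.10 commits to a 95% interval in each subgroup, an interaction p-value and ratios of ratios, for the primary outcome and the two key implementation outcomes. Country has four levels, so there are three interaction parameters, but no joint test is defined.

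**The concern.** The SAP recognises that country is a small-sample problem, but the correction it writes down barely acts. Counting df over all 78 facilities moves the critical value from 1.96 to 2.00. The quantity being estimated, the effect in one country, rests on that country's facilities: about 9 or 10 per arm in a country with 19, and 5 per arm in one with 10. An uncorrected sandwich variance is biased downward at such numbers, and it is also noisier than 65 df implies.

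At stake are the country-specific intervals and the heterogeneity p-value. Their stated role is to check consistency of effect across subgroups. A test that rejects well above its nominal level can report differences between countries that do not exist.

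**Working it through.** **1. The plan's own figure, to confirm the inputs.** SAP Appendix Table E8 gives 99.1% power for a 25% reduction from 4% with ICC 0.02, CAC 0.97 and 72 facilities.
- Births per facility-period: 192 × 7 = 1,344. Size-inflated: m' = 1,344 × (1 + 0.5²) = 1,680.
- 1 + (m' − 1) × ICC = 1 + 1,679 × 0.02 = 34.58.
- r = m' × ICC × CAC / 34.58 = 1,680 × 0.02 × 0.97 / 34.58 = 0.9425.
- Design effect = 34.58 × (1 − 0.9425²) = 3.86.
- SE = √[(0.04 × 0.96 + 0.03 × 0.97) × 3.86 / (36 × 1,344)] = 0.00232.
- z = 0.01 / 0.00232 = 4.31; power = Φ(4.31 − 1.96) = 99.1%. Reproduced.

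**2. Degrees of freedom under 7.10.** Fixed effects: intercept, period, exposure, country (3), births, oxytocin, exposure-by-country (3) = 11. Adding two variance components gives 13. So df = 78 − 11 = 67 or 78 − 13 = 65. t(65) = 1.997, and 1.997 / 1.960 = 1.019, a widening of 1.9%.

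**3. Facilities behind each country effect.** 78 / 4 = 19.5, so the smallest country has at most 19. With n − 2 df, t(17) = 2.110 (19 facilities), t(12) = 2.179 (14) and t(8) = 2.306 (10).

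**4. Simulation of the rule as written.** Inputs from the SAP: 78 facilities, 1,344 births per facility-period, size CV 0.5, prevalence 3.6%, ICC 0.018, CAC mainly 0.97. The true effect was the same in every country. The country splits are assumptions. Each scenario used 1,500 to 2,500 trials, analysed with a constrained-baseline mixed model on the logit scale (facility and facility-period effects), a facility-level sandwich × G/(G − 1), and the SAP df.

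| Split (assumed) | Coverage of 95% country interval | Joint 3-df rejection at 5% |
|---|---|---|
| 20/20/19/19 | 90-95% | 9-15% |
| 33/15/15/15 | 89-90% in smaller countries | 12-15% |
| 36/14/14/14 | 88-91% in smaller countries | 12-17% |
| 38/14/14/12 | 87-90% in smaller countries | 14-18% |
| 48/10/10/10 | 85-89% in smaller countries | 18-25% |

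The largest country in the uneven splits stays at about 92.5-95%. Single t tests of one country against the reference reject 7-14%.

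**5. Where the error comes from.** One 48/10/10/10 run (common period effect, 67 df), for a country with 10 facilities:
- The true SD of the estimate was 0.1349. The mean robust SE was 0.1110 (ratio 0.82) and coverage was 85.6%.
- The mean model-based SE was 0.1287 (ratio 0.95) and coverage with the same df was 94.0%.
- Joint rejection was 23.0% (robust), 6.0% (model-based) and 5.1% (bias-corrected sandwich with country-level df).

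Across scenarios, model-based SEs with the SAP df covered about 92-95% and rejected about 5-9.5%. Country-level df with the sandwich left uncorrected still covered only 90-94%.

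**6. Widening needed on the log scale.** Ratio = [t(n − 2) / 1.997] / (robust SE / true SD), over the simulated range of SE ratios:
- 19 facilities: 1.056 / 0.97 to 1.056 / 0.92 = 1.09 to 1.15.
- 14 facilities: 1.091 / 0.93 to 1.091 / 0.90 = 1.17 to 1.21.
- 10 facilities: 1.155 / 0.90 to 1.155 / 0.82 = 1.28 to 1.41.

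**7. Median-split facility subgroups.** With about 39 facilities per level, t(37) = 2.026 and 2.026 / 1.997 = 1.015. Simulated interaction rejection was about 5-7%.

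**8. After correction.** A bias-corrected sandwich with n − 2 df per country gave 94-97% coverage. The joint F test with denominator df of the smallest country minus 2 rejected 2-5%.

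**The case against.** The best defence is that the df rule is a recognised between-within method for mixed models with binary outcomes, and that 7.10 never says robust. This stands in part. A reader might infer that the df rule is itself the error. It is not: with model-based standard errors, which pool the variance components over all 78 facilities, it performs tolerably. But 7.10 adds a term to a model that 7.4 and 7.4.1 define with robust standard errors, so as written the two are paired. Model-based standard errors are not a free remedy either. Coverage fell to 86-88% in a country given four times the facility-period variance.

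Second, a reader might infer that false heterogeneity will be found two to four times too often. The documents do not support that without conditions. The upper end needs an uneven split such as 48/10/10/10, and it refers to a joint test that the SAP does not define.

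Third, the SAP already promises caution, reports subgroups whatever their significance, and rests no decision on them. That limits the consequence, but caution does not repair a miscalibrated interval. The Protocol's publication policy ("Individual countries will be allowed to publish their efficacy results") adds little, because nothing says such papers would use the pooled interaction model.

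Fourth, the simulations work on the logit scale. They do not reproduce marginally standardised risk ratios with unconditional standard errors, and they cover the primary outcome only. This is a fair limit on precision, not on direction.

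**Conclusion.** The concern holds for the country subgroup. The fault is the pairing of an uncorrected sandwich with trial-wide df. With equal numbers per country, the most favourable split possible, the effect is modest: coverage falls short by up to about 5 points and joint rejection is about two to three times nominal (9-15%). It is larger where the smaller countries have 10-15 facilities. All these sizes rest on assumed splits and on the SAP's prevalence, ICC and CAC.

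Two further readings should be resisted. The factors 1.09-1.15, 1.17-1.21 and 1.28-1.41 say how much wider the corrected intervals are. They do not say how much too narrow the planned ones are, which is 1 − 1/ratio: about 8-13%, 15-18% and 22-29%. Nor does the problem extend in any material way to facility size, baseline PPH rate or compliance, where splits of about 39 v 39 are near nominal. The primary analysis is untouched, and what is affected is supportive.

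**What to change.** In SAP 7.10, for country:
- State which standard error applies. Use a bias-corrected sandwich (Mancl-DeRouen or CR2) and, for each country-specific effect, a t-distribution with Satterthwaite df or the number of facilities in that country minus 2. Changing the df alone is not enough.
- Define heterogeneity as one joint 3-df F test using the same corrected variance and a small denominator df, for example the smallest country's facilities minus 2.
- If the Stata mixed logit cannot supply this, use facility-level baseline-adjusted contrasts with the same correction. Weight them by cluster size, so that they keep the participant-average target of 7.1 and match the weighting in 7.4.4.
- Report the number of facilities per country and arm beside the estimates.

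Applying the correction to the median-split subgroups is optional.

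The cost is SAP wording, a little programming, and country intervals that are wider by the factors in step 6. The joint test may be slightly conservative (2-5%).

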7.11. Supportive and sensitivity analyses

Sensitivity analyses will be limited to the primary composite outcome and key implementation outcomes and will consist of:

- Fully adjusted analysis
- Accounting for Missing Data (Missing at Random)
- Accounting for Missing Data (Missing Not at Random)
- Independent estimating equations (Informative clustering)

Fully adjusted Analysis

For the adjusted analysis, we will use a propensity score (PS) based method – the direct PS adjustment as recommended by Leyrat et al[16]. Under this method, the PS is obtained by fitting a multivariable logistic model with potential confounders (age; parity; multiple pregnancy; mode of birth; and birth weight) in the model, and treatment arm as the outcome. The PS is then the probability of being in the E-MOTIVE arm given these observed confounders. Clustering is not accounted for in the estimation of the PS as treatment arm is nested within cluster. Age and birthweight will be included as continuous covariates. For continuous covariates, we will model the relationship using fractional polynomials if they better depict the relationship than a linear trend, with a $p < 0.05$ threshold. Including continuous covariates with fractional polynomials is recommended when the relationship between covariate and outcome is not known [17]. Parity (none vs any), multiple pregnancy (singleton vs multiple), and mode of birth (spontaneous vs assisted) will be treated as binary. We will constrain the propensity

score for baseline observations to be zero - since no patient can receive intervention in that time period.

In the direct adjustment approach, the PS is then included in the analysis model as a covariate in its continuous form. We will include the PS with fractional polynomials if this better predicts the relationship with the outcome than including the PS in a linear form. We will use a $p < 0.001$ threshold for including fractional polynomial form.

The model fitted to the data for the sensitivity analysis will therefore include the minimisation parameters (as discussed in *Primary Analysis*, above), and a covariate for the propensity score.

As agreed in the DMC charter, at the 3rd DMC meeting (after approximately 75% of births), the DMC will be asked to consider whether there is any clear evidence of substantial selection bias. In the unlikely event that substantial selection bias is confidently identified, then the TSC and TMG will consider whether the sensitivity analysis (with PS) will become the primary analysis for all outcomes. Any decision will be documented in the meeting minutes.

Accounting for missing data

The potential for missing outcome data and missing covariate data is discussed in section 7.7. Below, we present multiple imputation methods to deal with missing outcome and individual-level covariate data. We consider this under two assumptions:

- 1) Data missing is missing at random (MAR)
- 2) Data missing is missing not at random (MNAR).

To evaluate the impact of missing data under MAR and MNAR mechanisms, multiple imputation will be used. We will impute the primary outcome (for all women who do not have source-verified primary outcome data) and individual level covariates (for any covariate used in the adjusted analysis).

Missing at Random

We firstly perform multiple imputation using chained equations [18]. The primary outcome and all covariates required for the adjusted analysis with missing data will be included in the imputation process. The following auxiliary variables will be included to aid the imputation process: country; cluster size (above or below median); Oxytocin quality (high or low); time period (baseline or post-randomisation); exposure to E-MOTIVE; previous C-section; gestational age; antepartum haemorrhage; retained placenta; and non-source verified blood loss.

The number of imputations, n , will be equal to the proportion of patients with any missing primary outcome data. To ensure inferences are valid, clustering will be allowed for in the imputation process. This will be done using BLIMP 3.0 which allow a random effect for cluster to be included [19].

In each imputed dataset, a propensity score is obtained by fitting a multivariable logistic model with potential confounders (age; parity; multiple pregnancy; mode of birth; and birth weight) in the model, and treatment arm as the outcome. In each imputed dataset, the analysis model with PS included in the model as a covariate is fitted and an estimate of the summary measure is obtained. The RR and RD will be obtained in the same manner as for the primary analysis – using marginal standardisation. The summary measure from each of the n imputed datasets is then pooled using Rubin's rules.

Missing Not at Random

An analysis to assess the effect of missing responses for the primary outcome only. This analysis will explore the possibility that missing responses are 'missing not at random' (MNAR) using a tipping point approach.

We firstly perform multiple imputation using chained equations [18]. The primary outcome and all covariates required for the adjusted analysis with missing data will be included in the imputation process. The following auxiliary variables will be included to aid the imputation process: country; cluster size (above or below median); Oxytocin quality (high or low); time period (baseline or post-randomisation); exposure to E-MOTIVE; previous C-section; gestational age; antepartum haemorrhage; retained placenta; and non-source verified blood loss.

The number of imputations, n , will be equal to the proportion of patients with any missing primary outcome data. To ensure inferences are valid, clustering will be allowed for in the imputation process. This will be done using BLIMP 3.0 which allow a random effect for cluster to be included [19].

For the MNAR mechanism, we will assume the prevalence of the primary outcome differs in those patients with a missing outcome compared to those patients with an observed primary outcome. To do this, we will include a parameter in the imputation process that shifts the expected prevalence (of the primary outcome) by a fixed amount. This "*missing parameter*" is a fixed value, and the magnitude and sign of the coefficient determines the strength and direction of the missing not at random process (see below). This parameter is included in each arm separately, to allow the MNAR mechanism to influence one arm at a time.

By selecting a variety of values of the missing parameter, we can identify the “tipping point”. This refers to the point in which general conclusion of the primary analysis changes. The tipping point will be determined in one of two ways:

Option A: The CI in the primary analysis does not contain one for the risk ratio (i.e., one treatment is superior to the other), then the point in which the CI crosses one will be highlighted (the tipping point). The base case from the primary analysis will be highlighted.

Option B: The CI in the primary analysis does contains one for the risk ratio (i.e., inconclusive whether one treatment is superior to the other), then the point in which the CI no longer contains one will be highlighted (the tipping point). The base case from the primary analysis will be highlighted.

We will consider two scenarios: MNAR in exposed arm only (i.e., those in E-MOTIVE arm in the post-randomisation period) and MNAR in non-exposed arm only (i.e., those in standard care arm and those in baseline period).

MNAR in exposed arm only

Firstly, we assume that all patients in the unexposed group with missing outcome data have the same prevalence as those who are observed. In the exposed group, we will set the *missing parameter* to change the prevalence of the outcome in those with missing outcome data in the exposed group. We will estimate the effect measure using n imputation, by fitting a model with exposure, time period and cluster-level covariates to each imputed dataset separately. The RR and RD will be obtained in the same manner as for the primary analysis – using marginal standardisation. The summary measure from each of the n imputed datasets is then pooled using Rubin’s rules. The effect measure and CI will be examined and stored. We will use several values of the *missing parameter* to visualise how the effect measures and confidence intervals change as the prevalence of the outcome in those with missing data changes.

MNAR in unexposed arm only

Firstly, we assume that all patients in the exposed group with missing outcome data have the same prevalence as those who are observed. In the unexposed group, we will set the *missing parameter* to change the prevalence of the outcome in those with missing outcome data in the unexposed group. We will estimate the effect measure using n imputation, by fitting a model with exposure, time period and cluster-level covariates to each imputed dataset separately. The RR and RD will be obtained in the same manner as for the primary analysis – using marginal standardisation. The summary measure from each of the n imputed datasets is then pooled using Rubin’s rules. The effect measure and CI will be examined and stored. We will use several values of the *missing parameter* to visualise how the effect measures and confidence intervals change as the prevalence of the outcome in those with missing data changes.

Independent estimating equations

Informative cluster sizes may impact the estimate of the effect measure. In the primary analysis methods, we have included a country-centred binary covariate to indicate cluster size. An alternative approach would be to have fitted independent estimating equations – though this reduces power. Therefore, as a sensitivity analysis, we will fit a generalised estimating equation with independent working correlation. We will use log links and identity links to obtain estimates of the risk ratio and risk difference. This is to test whether our approach is robust to informative cluster sizes. This sensitivity analysis was recommended by the statistician from the Data Monitoring Committee.

8. Statistical software

[figure not shown]
Statistical analysis will be undertaken in the following statistical software packages: Stata.

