7.4.2. Primary outcome - accounting for baseline period

The analysis will use a constrained baseline analysis approach, as recommended by Hooper et al[8]. Here, outcomes collected during the baseline period and the post-randomisation period are treated as longitudinal and a repeated measures analysis is used to estimate the summary measure.

Under this approach, there are two binary covariates included as fixed effects in the model: (i) period and (ii) exposure to E-MOTIVE. These covariates are described below.

Covariate for period

A binary variable will indicate whether observations are taken from the baseline period (0) or the post-randomisation period (1) of the study.

Covariate for exposure to E-MOTIVE

A binary 'treatment' variable will indicate whether observations are exposed to the E-MOTIVE bundle. That is, observations taken in the post-randomisation period in clusters allocated to E-

MOTIVE will have a value of 1, and all other observations (control clusters and E-MOTIVE clusters during baseline phase) will have a value of 0. This binary treatment variable will be used to determine the impact of the intervention. Under this approach, it is assumed that there is no systematic differences between the groups at baseline.

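### Setting the propensity score to zero for all baseline births over-corrects the fully adjusted analysis when a case-mix difference between arms is present in both periods

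*SAP*

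**What the plan says.** SAP 7.11 fits a logistic model for treatment arm on five individual covariates: age, parity, multiple pregnancy, mode of birth and birth weight. It defines the result: "The PS is then the probability of being in the E-MOTIVE arm given these observed confounders". It then constrains the propensity "score for baseline observations to be zero - since no patient can receive intervention in that time period". In the outcome model "the PS is then included in the analysis model as a covariate in its continuous form", and that model "will therefore include the minimisation parameters (as discussed in *Primary Analysis*, above), and a covariate for the propensity score". No other individual case-mix term is listed.

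The outcome model is the constrained baseline model of SAP 7.4.1 and 7.4.2, in which "outcomes collected during the baseline period and the post-randomisation period are treated as longitudinal". It has random facility and facility-by-period effects, no arm difference at baseline, and a period term: "A binary variable will indicate whether observations are taken from the baseline period (0) or the post-randomisation period (1) of the study".

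SAP 7.11 also provides that, if the Data Monitoring Committee confidently identifies substantial selection bias at its third meeting, the TSC and TMG "will consider whether the sensitivity analysis (with PS) will become the primary analysis for all outcomes".

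**The concern.** The reason given for the zero is about exposure: nobody could receive E-MOTIVE at baseline. The score as defined is about arm membership given covariates. A baseline birth in an E-MOTIVE facility has covariates and an arm, so that probability is not zero.

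The consequence is an asymmetry. Every baseline birth has the same score, so the period term absorbs the jump from zero and the score adjusts case mix among post-randomisation births only. Baseline rates enter unadjusted. If E-MOTIVE facilities have more high-risk women in both periods, the baseline rates already remove most of that excess, and the score then removes it again.

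At stake is the analysis meant to show whether selection has distorted the result. A gap between it and the primary analysis could be read as evidence of selection when the zero rule had produced the gap. The model could also become primary.

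**Working it through.** **Inputs from the documents**
- 78 facilities, 1:1 (SAP 4.3)
- 192 births per facility per month over 7 months, so m = 192 × 7 = 1,344 per facility-period (SAP 4.7)
- Baseline prevalence 3.6%, ICC 0.018 observed and 0.02 planned, cluster autocorrelation (CAC) 0.97 or 0.99 (SAP 4.7)
- Coefficient of variation (CV) of cluster size 0.5, 72 facilities (note to the SAP power table)

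**Assumed:** the size of the case-mix imbalance and the strength of the factor. The documents give neither.

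**1. Check of the inputs against the plan's own power.** For 4% v 3%, ICC 0.02, CAC 0.97 and m' = 1,344 × (1 + 0.5²) = 1,680:
- Design effect = 1 + 1,679 × 0.02 = 34.58
- r = 1,680 × 0.02 × 0.97 / 34.58 = 0.9425, so 1 - r² = 0.1117
- Effective n per arm = 36 × 1,344 / (34.58 × 0.1117), about 12,530
- Power = 99.1%, as the table states

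**2. Weight on the baseline rate.** r = m × ICC × CAC / (1 + (m - 1) × ICC). At ICC 0.018 and CAC 0.97:
- m = 1,344: 23.47 / 25.17 = 0.93
- m' = 1,680: 29.33 / 31.22 = 0.94

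With m = 1,344, r runs from 0.89 to 0.99 over ICC 0.01 to 0.05 and CAC 0.95 to 1.0.

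**3. Algebra (linear approximation).** The estimator is about the post-randomisation arm difference minus r times the baseline arm difference. Let τ be the true effect and D the outcome effect of a case-mix difference present in both periods.
- No score (planned primary): τ + D - rD = τ + (1 - r)D
- Score zero at baseline: τ + (D - D) - rD = τ - rD
- Case mix adjusted in both periods: τ + (D - D) - r(D - D) = τ

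With D = ln(odds ratio) × imbalance and r = 0.93, the predicted log-odds-ratio bias under the zero rule is:
- odds ratio 2, 10 points: -0.93 × 0.0693 = -0.064
- odds ratio 3, 10 points: -0.93 × 0.1099 = -0.102
- odds ratio 1.5, 5 points: -0.93 × 0.0203 = -0.019

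**4. Simulation.** Logistic mixed model with both random effects and marginal standardisation; 78 facilities, CV 0.5, prevalence about 3.5 to 4%, ICC about 0.02, CAC 0.97; 300 replicates per scenario. There is one binary factor. Minimisation covariates and robust standard errors are omitted. Entries are geometric mean risk ratios.

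| Scenario | True | No score | Zero rule | Both periods |
|---|---|---|---|---|
| Both periods, 45% v 35%, OR 2 | 1.000 | 1.007 | 0.942 | 1.003 |
| Both periods, 45% v 35%, OR 3 | 1.000 | 1.013 | 0.913 | 1.005 |
| Both periods, 40% v 35%, OR 1.5 | 1.000 | 1.004 | 0.984 | 1.002 |
| Both periods, 45% v 35%, OR 2 | 0.753 | 0.760 | 0.710 | 0.758 |
| After randomisation only, 45% v 35%, OR 2 | 1.000 | 1.071 | 1.001 | 1.002 |
| Chance imbalance, OR 2 | 1.000 | 1.001 | 0.999 | 0.999 |

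Under the zero rule, the log-odds-ratio bias in the first three rows is -0.063, -0.097 and -0.017, close to step 3. With 150 replicates, CAC 0.99 gives 0.944 for the first row and a much lower ICC gives 0.965.

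In the last row the mean is right, but the zero-rule error correlates -0.18 with the realised imbalance, against 0.00 when both periods are adjusted.

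**The case against.** The strongest reply is that the striking figures come from fixing an unlikely imbalance. If facility prevalences of the factor have an assumed SD of 15 points, the standard error of the difference between 39 and 39 facilities is 15 × √(2/39) = 3.4 points. A 10-point gap is then 2.9 standard errors, with two-sided probability about 0.003. In a facility-level simulation with chance imbalance at that SD (700 replicates), type I error was 5.6% under the zero rule, 5.9% with no score and 5.9% with both periods adjusted for odds ratio 2. For odds ratio 3 it was 5.3%, 5.9% and 6.3%. This stands: over randomisations the cost is precision, with an SD roughly 7 to 17% larger, and not false positives.

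It is also true that the rule is unbiased for imbalance arising only after randomisation, which is the selection the analysis targets. Promotion is described as unlikely and is only to be considered. Characteristics are tabulated by arm and period (SAP 6.5), so a stable imbalance would be visible. But adjusting both periods handles post-randomisation selection equally well, so the zero rule gains nothing. SAP 7.11 also does not require the imbalance to be absent at baseline before promotion is considered. Minimisation on the baseline outcome rate is no protection, because case mix is not a minimisation factor.

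A reader might infer two further faults that the documents do not support:
- **Imputation.** The score is not part of the missing-at-random imputation model. Imputation uses chained equations with listed auxiliary variables. The score enters only the analysis model fitted afterwards, and that text does not restate the zero rule.
- **Fractional polynomials.** SAP 7.11 says "We will include the PS with fractional polynomials if this better predicts the relationship with the outcome", and log or negative powers are undefined at zero. But the score is constant at baseline and the period term absorbs whatever constant is used, so this is a coding detail.

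**Conclusion.** The point holds conditionally. Given a case-mix difference present in both periods, the fully adjusted estimate is over-corrected by about -rD, with r about 0.93 to 0.94. At a true risk ratio of 1.00 that means about 0.94 or 0.91 for an assumed 10-point imbalance (odds ratio 2 or 3), and about 0.98 for 5 points and odds ratio 1.5. The shift is smaller at a much lower ICC. These sizes rest on the assumed imbalance and factor strength, and on a simulation simpler than the planned five-covariate score.

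A reader might conclude that the adjusted analysis is biased as a rule, or that the trial's primary result is. Neither follows. Under randomisation the mean bias is near zero, and the primary model in SAP 7.4 contains no score. From bias and SD, the two 10-point cases imply rejection rates of about 16% and 30%. Those rates are conditional on the assumed imbalance and are not the trial's type I error.

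This should be fixed because the analysis is the plan's check on selection and may become primary. It is not a fault in the primary analysis.

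**What to change.** In SAP 7.11, delete the zero constraint. State that the score is estimated in post-randomisation births and then evaluated, from the fitted model, at each woman's own covariates in both periods. Keep the period and exposure terms unchanged. An alternative, not identical, is to enter the five covariates directly in the outcome model for all births. State that the same rule applies to the score-adjusted model fitted in the imputed datasets.

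The cost is about two sentences and a few lines of code. SAP Appendix E3 already tabulates these covariates for both periods, so no new data are needed.
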